**Pre-Screening:** Participants responding to recruitment efforts (see pages 35-36) will be screened by telephone. If participants prefer to answer some of the screening questions through the Yale Qualtrics system, participants will indicate their consent to the recruitment/screening process in the online system. Potentially eligible participants will be consented and evaluated in-person by trained supervised research clinicians (doctoral level and/or advanced trainees). Participants will complete survey measures of eating behaviors and psychopathology and psychosocial functioning around the time of the in-person appointment.

[figure not shown]
Participants who provide informed consent and are determined to be eligible (see page 15-16) will then participate in the study as depicted and described in the following paragraphs. See also Figure 1 (page 8).

**Stage 1**, N=180 patients with BED and obesity will be randomized to one of three 12-week treatments: CBT, LDX, or CBT+LDX.

**In Stage 2**, patients who received pharmacotherapy (Stage1 LDX or CBT+LDX) and were “Responders” (defined as 65% or more decrease in binge eating) will be randomly assigned in equal proportions (blocked randomization stratified by first treatment) to LDX or placebo (double blind) for 12 weeks.

“Non-responders” to Stage 1 pharmacotherapy (LDX or CBT+LDX) will be randomized to a second medication (NB or placebo) in double-blind fashion for 12 weeks. Stage 1 CBT patients will be followed without further treatment; this will allow controlled comparison of Stage 1 RCT and context for Stage 2 RCTs.

Independent assessments will determine outcomes after discontinuation of treatments through 18 months. Secondary aims are to produce important new data regarding predictors of outcomes and moderators of treatment effects to inform prescription (i.e., for whom LDX vs. CBT work best), and exploration of potential mediators through which the distinct treatments achieve outcomes, and cost-effectiveness estimates.

**Figure 1.** Study design

Potential participants will be screened by telephone and potentially eligible patients will be consented and evaluated in-person by trained supervised research clinicians (doctoral level and/or advanced trainees). (see page 36).

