**Randomization to Stage 1 Treatment.** Eligible participants who provide written informed consent will be randomized in equal proportions to one of three treatments (blocked randomization with random block sizes of 3 and 6 for Stage 1 to obviate any secular trends). Randomization will be stratified by two variables to be tested as moderators (overvaluation of shape/weight (based on  $\geq 4$  EDE item scores) and depression (based on  $> 16$  BDI-II score) ([name], Masheb, Crosby, 2012).

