**Randomization to Stage 2 Treatments for LDX and CBT+LDX (Stage 1) “Responders”.**

“Responders” to Stage 1 LDX (i.e., LDX and CBT+LDX) treatments will be defined as 65% or greater reduction in binge-eating. This cut-point is based on reliable findings regarding prognostic significance of such reductions ([name] et al., 2006; 2012) and supported by recent report on “time course of the effects of LDX” (McElroy et al., 2017). “Responders” will be randomized in equal proportions (using stratified blocked randomization with Stage 1 treatment as a stratifying variable) to LDX or placebo (double-blind) for 12 weeks.

**CBT Treatment Protocol.** CBT will be delivered by trained and monitored research clinicians following manualized protocols we have used successfully in previous RCTs (e.g., [name] et al., 2005, [name] et al., 2011). CBT will be delivered in individual sessions weekly for 12 weeks following CBT manuals based on Fairburn et al (1993) used in our RCTs ([name] et al., 2005, 2011) which are similar to those used in major RCTs testing CBT delivered via 12-24 weeks (Wilfley et al., 2002; Wilson et al., 2010). The CBT manuals provide detailing session-by-session procedures for clinicians and parallel guides are provided to the patients to facilitate homework and mastery of the material. CBT, a specialist focal treatment, consists of

three overlapping phases. Phase one involves establishing a collaborative therapeutic relationship while focusing on educating the patient about the nature of binge-eating and factors thought to maintain the problem. Specific behavioral strategies (e.g., self-monitoring) are used to help patients identify problematic eating patterns while establishing a normal structured eating pattern. Phase two integrates cognitive restructuring procedures, where patients learn to identify and challenge maladaptive cognitions regarding eating and weight/shape and thoughts that trigger binge-eating. Phase three focuses on maintenance of change and relapse prevention.

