**LDX Pharmacotherapy Treatment Protocol.** Medication will be double-blind; patients and study staff, physicians and investigators will be blind to medication assignment. **LDX, FDA-approved for BED**, will be prescribed per procedures found to be superior to placebo in two large-scale phase 3 RCTs (McElroy et al., 2015). The LDX (dose-optimization at 50-70mg per day) protocol followed the McElroy et al (2015) RCT findings that 50-70mg/day dosing was significantly superior to 30mg/dosing and to placebo.

During week 1, LDX will be 30 mg/day for initial titration. During week 2, LDX will be titrated to 50mg/day. During weeks 3-4, LDX increases to 70mg will be made based on acceptable tolerability and clinical need. If 70mg is not tolerated, downward titration to 50mg/day can occur. For the remaining treatment (weeks 4-12), the optimized LDX dose (50 or 70 mg/day) will be maintained.

For the Stage 2 randomized maintenance (double-blind) treatment, a similar approach to dose-optimization will be followed for responders. "Responders" re-randomized to LDX will continue taking LDX at the same dose as Stage 1. "Responders" randomized to placebo will be switched from LDX to placebo. Participants will be instructed to take the medication (active or placebo) once daily in the morning.

Safety and tolerability will be assessed during study clinic visits as will clinical compliance with the study medication. During the dose-optimization period, if the patient develops tolerability concerns, dosing can be reduced once to achieve tolerability. If the patient cannot tolerate the medication, has adverse effects, or is non-compliant with medication for > 7 consecutive days, s/he will be discontinued from the medication arm. Physician visits will be brief (10-15 minutes) and focus on compliance with dosing and evaluating side effects without integrating dietary, behavioral, or CBT techniques.

In Stage 1 or Stage 2, participants taking medication for greater than 4 weeks, a taper will be provided (Refer to Minimizing Risk section on page 20 for details).

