### DATA ANALYSIS

Baseline demographic and clinical characteristics for randomized groups will be compared using chi-square tests for categorical variables, and ANOVA or Kruskal-Wallis tests for continuous variables. Continuous variables will be examined for adherence to normal distribution using normal probability plots and Kolmogorov-Smirnov tests. If normality not satisfied and transformations do not help with achieving normality, alternative analytic strategies will be considered such as generalized estimating equations or nonparametric methods. Dropouts and completers will be compared. Analyses will be intent-to-treat; patients will be followed regardless of treatment completion to minimize missing data. Primary outcomes will be tested at two-sided 0.05 significance level. Secondary analyses will be adjusted for multiple tests using Bonferroni correction.

Overall Data Analysis Strategy will involve MIXED EFFECTS MODELS (Diggle et al, 2002, Gueorguieva & Krystal, 2004) to compare treatments. These models allow for different numbers of observations per subject, use all available data on each subject, and are unaffected by randomly missing data. Further advantage is capacity to test and account for individual-difference contributions to treatment outcomes (Cudeck, 1996; Cudeck & Klebe, 2002; Hedeker et al., 1996; Hedeker & Gibbons, 1996; Singer, 1998). They provide flexibility in modeling the correlation structure of data. In models for each outcome, we will include fixed effects of time, treatment, and interaction between time and treatment, and random subject-level effects. Because we cannot a priori predict the shape of responses over time in each arm of the trial we will first treat time as a categorical predictor and will then test for polynomial trends over time. We will consider different error structures (e.g., AR1, independence) and select the best fitting one based on information criteria. We will

compare dropout patterns between groups and if there are concerns of informative dropout or informative intermittent missing data, we will use pattern mixture models (Hedeker & Gibbons, 1997) to perform sensitivity analyses.

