**(5) Secondary Aim:** Generate estimates of cost-effectiveness. We will compute within-study costs for CBT, LDX, CBT+LDX and SMART Stage 2 interventions. Repeated assessments will track additional clinician visits and medication use in our RCT as well as outside treatment contacts through the 18-months. SF-12, administered pre- and post-treatments and at follow-ups, will be used to calculate quality-adjusted life years (QALY) following established methods (Revicki et al., 2005) also used in BED studies of cost-effectiveness specifically of LDX (Agh et al., 2016) and CBTgsh (Lynch et al., 2010; Dickerson et al., 2011), as well as for obesity (Tsai et al., 2005; Malone et al., 2005) including obesity medications (Ara et al., 2012), and for similar SMART designs (switching medication for initial non-responders) in depression (Singh et al 2017). We will calculate incremental cost-effectiveness ratios (ICERs) for the various arms; in these ICERs, the numerator will be the incremental medical cost and the denominator will be the incremental effectiveness of the specific treatment compared to CBT. Confidence intervals for the ICERs will be determined using non-parametric bootstrapping. These ICERs will be compared to the two previous BED (Agh et al., 2016; Lynch et al., 2010) analyses and inform subsequent more definitive larger-scale effectiveness studies.

**POWER ANALYSIS:** We calculated our sample size to have at least 80% power at 2-tailed alpha level 0.025 (adjust for 2 outcomes) to detect clinically meaningful effects in Stage 1 for co-primary outcomes (binge eating and weight loss) and Stage 2 for primary outcome (relapse by initial Responders) at 2-tailed level of 0.05 according based on documented effects of the two treatment components (LDX and CBT). In Stage 1, with 180 subjects total (60 per treatment group), accounting for up to 20% dropout, we can detect medium effect sizes ( $d=0.64$ ,  $f=0.32$ ) for the between group comparisons with more than 80% power at two-sided alpha level of 0.025. These effect sizes are smaller than the effect sizes calculated based on data (Telch et al., 1990; [name] et al., 2005; McElroy et al., 2015, McElroy 2016) which ranged  $d=0.69$  to  $d=0.78$  for the comparison of CBT to LDX on binge-eating and was  $d=1.53$  for LDX vs CBT on percent weight loss. Dropout

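### CBT clinicians treat participants in two of the three arms but the model has no therapist term: if therapists differ, the standard error of the CBT-containing versus LDX contrasts on binge eating is too small

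*Combined protocol and SAP*

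**What the plan says.** Stage 1 participants are "randomized to one of three 12-week treatments: CBT, LDX, or CBT+LDX", and two of those arms contain CBT. The CBT Treatment Protocol states that "CBT will be delivered in individual sessions weekly for 12 weeks" and that "CBT will be delivered by trained and monitored research clinicians following manualized protocols". It does not say how many clinicians there are or how participants are assigned to them. Under the LDX Pharmacotherapy Treatment Protocol, "Physician visits will be brief (10-15 minutes) and focus on compliance with dosing and evaluating side effects", with CBT techniques left out.

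The Overall Data Analysis Strategy in section 13 states for each outcome: "we will include fixed effects of time, treatment, and interaction between time and treatment, and random subject-level effects". It adds: "We will consider different error structures (e.g., AR1, independence) and select the best fitting one based on information criteria". Those structures describe repeated measurements on one person, not different people who share a therapist.

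Stage 1 randomization is stratified by overvaluation of shape/weight and by depression, not by clinician. The Power Analysis claims "we can detect medium effect sizes" (d = 0.64) with more than 80% power at two-sided 0.025, from 60 per arm less 20% dropout. No therapist ICC, design effect, therapist term or therapist sensitivity analysis appears anywhere.

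**The concern.** Participants treated by the same therapist may have outcomes more alike than participants treated by different therapists. Here that source of correlation exists in the two CBT-containing arms and is absent from the LDX arm. A model with subject-level effects only has no place for it, so part of any difference between therapists is read as evidence about CBT.

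The contrasts exposed are the ones the plan relies on: its Stage 1 hypothesis for binge eating is that CBT and CBT+LDX each reduce it more than LDX. If therapists differ, the confidence intervals for those contrasts are too narrow and the tests reject too often under the null.

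CBT versus CBT+LDX raises a different issue. If clinicians are spread unevenly over these two arms, the comparison is partly one of clinicians. Nothing in the randomization or treatment sections prevents that.

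**Working it through.** **Inputs from the documents.** 60 per arm and 20% dropout give 60 × 0.8 = 48 evaluable per arm. d = 0.64 and two-sided alpha 0.025 come from the Power Analysis. The Data Analysis section tests primary outcomes at 0.05, so both levels are shown.

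**Assumed inputs, not in the documents.** 4 to 10 therapists (k), ICC 0.02 to 0.05, equal caseloads, and no clustering in the LDX arm.

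**Step 1: the plan's own figure.** The standardised difference is 0.64/√(2/48) = 3.135 and the critical value is 2.241. Power = Φ(3.135 − 2.241) = 0.814, or 0.803 with the noncentral t. This agrees with the stated figure of more than 80%, and it treats all participants as independent.

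**Step 2: standard error with therapists.** In a CBT-containing arm the design effect is DE = 1 + (48/k − 1) × ICC. For a contrast with LDX, the true standard error divided by the modelled one is R = √((DE + 1)/2).
- k = 10, ICC 0.02: DE = 1 + 3.8 × 0.02 = 1.076; R = 1.019.
- k = 6, ICC 0.05: DE = 1 + 7 × 0.05 = 1.35; R = 1.084.
- k = 4, ICC 0.05: DE = 1 + 11 × 0.05 = 1.55; R = 1.129.

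**Step 3: actual error rate and power.** The planned test has type I error 2(1 − Φ(z/R)) and power Φ((3.135 − 2.241)/R).

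| k, ICC | R | Actual error at 0.025 | Actual error at 0.05 | Power of planned test |
|---|---|---|---|---|
| any, 0 | 1.000 | 0.025 | 0.050 | 0.81 |
| 10, 0.02 | 1.019 | 0.028 | 0.054 | 0.81 |
| 6, 0.05 | 1.084 | 0.039 | 0.071 | 0.80 |
| 4, 0.05 | 1.129 | 0.047 | 0.083 | 0.79 |

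Simulation with 40,000 runs per setting gave 0.0386 (k = 6) and 0.0486 (k = 4) at ICC 0.05 and nominal 0.025, close to the formula. Outside the assumed range, 4 therapists with ICC 0.10 would put the 0.025 test at about 0.072.

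**Step 4: CBT versus CBT+LDX.** When the same clinicians treat both arms evenly, a therapist's effect cancels in the difference. Simulated type I error at nominal 0.025 was 0.019 to 0.025, so not inflated.

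**Step 5: what a therapist random effect would cost.** With the corrected standard error but normal critical values, power at d = 0.64 is Φ(3.135/R − 2.241): 0.80 for k = 10 and ICC 0.02, and 0.70 for k = 4 and ICC 0.05. The normal critical value is too generous with few therapists. Satterthwaite degrees of freedom, (DE/48 + 1/48)² / [(DE/48)²/(k − 1) + (1/48)²/47], at ICC 0.05 are:
- k = 4: about 7.9; noncentral t power about 54%.
- k = 6: about 14.3; noncentral t power about 65%.

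**The case against.** The strongest reply is that the size is unknown and may be negligible. CBT is manualised session by session, and clinicians are trained, monitored and supervised, all of which may shrink therapist differences. At the mild end of the assumed range the standard error moves by 2% and the 0.025 test runs at 0.028. Treating therapists as this trial's fixed delivery team rather than as a sample is also a defensible inferential choice. This stands as a reason to word the point conditionally. It is not a reason to assume an ICC of exactly zero without recording who treated whom.

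A reader might infer several stronger things that the documents do not support:
- **That the planned standard error is definitely wrong.** It is wrong only if the ICC is above zero, and no ICC is given.
- **That the planned trial's power falls to about 70%.** That figure belongs to a test using the corrected standard error. The planned test keeps 0.79 to 0.81.
- **That the therapist team is small.** The protocol says only that research clinicians deliver CBT.
- **That the CBT versus CBT+LDX test is also too liberal.** With clinicians shared evenly it is not. Confounding there needs an uneven spread, which the documents neither show nor rule out.
- **That the LDX arm is free of all provider clustering.** Physicians see participants in both medication arms, and the placebo safeguards in Section II give all participants monthly visits with research clinicians. The documents do not show whether this matters.

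The scope is also limited. The weight contrast assumes d = 1.53, and its power stays above 99% even with 3 therapists and ICC 0.10, although its intervals would be affected if therapists influence weight. The Stage 2 relapse comparison of LDX with placebo is re-randomized within strata of Stage 1 treatment and is not a CBT contrast.

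**Conclusion.** The point holds in conditional form. The plan has therapist-delivered treatment in two of three arms, no therapist term and no rule for assigning clinicians. If the therapist ICC is above zero, the modelled standard errors for the two binge-eating contrasts with LDX are too small.

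Under the stated assumptions the harm is to the error rate and the intervals, modest at one end and near a doubling of the nominal 0.025 level at the other. It is not a loss of power in the planned analysis. Whether CBT versus CBT+LDX is confounded with therapist cannot be judged without an assignment rule or a record of the treating clinician. This warrants a low-cost addition to the plan, not a change of primary model.

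**What to change.** 1. Record the treating CBT clinician for every participant in the CBT and CBT+LDX arms.
2. Have each clinician treat participants in both arms in roughly equal numbers, and state this rule in the protocol.
3. Keep the planned primary model. Pre-specify a sensitivity analysis of the Stage 1 binge-eating contrasts with a therapist random effect that applies only in the CBT-containing arms (a partially nested model), using small-sample degrees of freedom such as Kenward-Roger. Report the estimated therapist variance beside the primary result.

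The cost is one data field, an assignment rule and one extra model in the SAS procedures already planned. The downside is imprecision when therapists are few, as Step 5 of the working shows (about 54% power with 4 therapists and 65% with 6, at ICC 0.05). The therapist variance would itself be poorly estimated in that case. That is why this analysis should accompany the primary model and not replace it. If participants have already been assigned to clinicians, items 1 and 3 can still be done provided the treating clinician can be identified from study records.

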FDA-Approved LDX (CNS Stimulant) Medication for BED An important recent development was the FDA approval in January 2015 of a CNS stimulant, lisdexamfetamine dimesylate (LDX), for the treatment of moderate-to-severe BED based on findings from an integrated series of studies funded by Shire (the manufacturer). The phase II (11-week) RCT demonstrated dosing response and that 50mg and 70mg were superior to placebo (McElroy et al., 2015). Two identically designed phase III RCTs testing LDX (50–70 mg dose optimization) for moderate-to-severe BED in adults (McElroy et al., 2016) found LDX superior to placebo for reducing binge-eating days and reported binge-eating abstinence rates of LDX versus placebo (Study 1: 40% versus 14%; Study 2: 36% versus 13%) at the end of 11 weeks of treatment. Primary analyses of reduction in binge-eating frequency significantly favored LDX over placebo in both phase-III RCTs, with effect-size of 0.83 and 0.97 (McElroy et al., 2016). Another much smaller RCT with N=50, also funded by Shire, reported weaker advantage of LDX over placebo (ES = 0.50), suggesting the need for further and continued investigation by other researchers. McElroy et al (2017) reported time-course data for binge-eating and associated outcomes to expand upon the McElroy et al (2015) report regarding the significant reductions (over 80%) in binge-eating with LDX; these analyses suggest an early and rapid response (and are supportive of our proposed definition of “response” (see Research Design section). The efficacy and safety data were reviewed and appear to represent a favorable benefit-to-risk ratio (Citrome, 2015).

LDX was also associated with significant acute weight loss relative to placebo (mean 4.9 kg) (McElroy et al., 2015, 2016); weight loss was examined as a safety measure. The FDA-approval and manufacturer product labeling include a “Limitation of Use” highlighting that LDX is not indicated for weight loss. In the present study, we anticipate that LDX will produce short-term weight loss and the key and novel research goals will involve the questions of the utility of maintenance LDX treatment and longer-term follow-up.

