(1) **STAGE 1 – Primary Outcomes Aim 1 and Secondary Outcomes Aim 2a:** Compare LDX and CBT effects, alone and in combination, for acute BED outcomes. Analyses examining the co-primary outcomes (reduction in binge-eating and percent weight loss) and examining the secondary outcomes (binge remission, eating disorder psychopathology, depression, metabolic variables) will be intent-to-treat using mixed-effects models per the overall strategy described above. Mixed-model analyses on continuous (or pseudo-continuous) data will use SAS PROC MIXED; mixed-model analyses on binary variables will use SAS PROC GLIMMIX. Logistic regression will be used for categorical outcomes (i.e., remission from binge-eating (defined as 0 binges/past 28 days on EDE interview). Significantly greater reductions in binge eating in CBT and CBT+LDX groups compared to LDX, and weight loss in LDX and CBT+LDX compared to CBT will be considered supportive of our primary aim hypotheses. We do not anticipate significant differences between CBT and CBT+LDX on binge eating and between LDX and CBT+LDX on weight loss but the mixed model approach will allow us to estimate the magnitude of the effects with associated confidence intervals.

(2) **STAGE 1 – Secondary Outcomes Aim 2b:** Explore conceptually and empirically supported predictors, moderators, and mediators for the primary outcomes (reductions in binge-eating and weight loss) and secondary categorical outcome (binge-eating remission). We will use the Kraemer et al (2002) approach to assess predictor, moderator and mediator effects by adding potential predictor, moderator and mediator variables to the models above. Predictors will be identified as variables with significant main effects on the outcome, moderators as variables with significant interactions with treatment on the outcome, and mediators will need to be significantly affected by treatment, to be related to the outcome and have main or interactive effects with treatment on the outcome. We will explore two empirically-supported predictors and moderators of BED outcomes – overvaluation of shape/weight (EDE) and depression (BDI-II) ([name], Masheb et al., 2012; [name] et al., 2013). It is necessary to test previous findings to establish them specifically for CBT and LDX treatments to inform prescription (i.e., for whom these “leading” treatments work best).

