rate estimated based on completion rates for [name] RCTs with BED: 87% in [name] & Masheb, 2005; 84% in [name], White et al., 2014; and previous grant 2R01 DK49587-15 testing stepped care multi-modal treatment and obesity medication along with the LDX RCTs (McElroy et al., 2015, 2016). For binary outcomes (remission), we can detect the following clinically meaningful differences in proportions (63% vs 35%, 66% vs 38%) at 2-tailed alpha of 0.025 in Stage 1. These are in line with observed proportions for CBT (62% by Wilson et al (2010); 64% by Striegel-Moore et al. (2010); LDX (40% and 36% by McElroy et al (2015; 2016) in BED subjects uncomplicated by co-morbidity. Thus, we are well powered for realistic and meaningful effect sizes for both primary and secondary outcome variables. In Stage 2, we expect to randomize 65-70% of subjects as Responders (per McElroy et al 2017); thus we anticipate to have about 80 subjects from the LDX and CBT+LDX groups for the comparisons of interest. Assuming further 20% dropout, we will have 64 subjects with complete data at the end of Stage 2. With this sample size, we have 89% power at two-sided alpha level of 0.05 to detect differences in relapse reported by Hudson et al (2015) of 4% vs 32% (LDX vs placebo). We would have over 80% power to detect differences for the following rates between placebo and LDX: 10% vs 39%, 15% vs 46%, 25% vs 58%.

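### Stage 1 remission is given two models and no rule for a missing month-3 EDE, so an analysis labelled intent-to-treat in effect covers only those interviewed

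*Combined protocol and SAP*

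**What the plan says.** All references are to the combined protocol and SAP.

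- **Outcome.** Remission means no binge episodes over 28 days on the EDE interview (section 4, Assessment of Treatment Outcome and Time Course; section 13, item 1). The Figure 2 grid places the EDE at baseline, month 3, month 6 and the two follow-ups. The self-report EDE-Q-I and BDI-II are collected monthly.
- **Model.** Section 13, item (1), lists remission among the secondary outcomes to be analysed by intent-to-treat mixed models and names PROC GLIMMIX for binary variables. It then says: "Logistic regression will be used for categorical outcomes (i.e., remission from binge-eating (defined as 0 binges/past 28 days on EDE interview".
- **Principle.** The opening paragraph of Data Analysis says: "Analyses will be intent-to-treat; patients will be followed regardless of treatment completion to minimize missing data". The next paragraph adds pattern mixture models as a sensitivity analysis if informative dropout is a concern.
- **Power.** The aim is "at least 80% power at 2-tailed alpha level 0.025 (adjust for 2 outcomes"). The allowance is "In Stage 1, with 180 subjects total (60 per treatment group), accounting for up to 20% dropout". For remission the detectable contrasts are "differences in proportions (63% vs 35%, 66% vs 38%) at 2-tailed alpha of 0.025 in Stage 1".
- **Anticipated rates.** "These are in line with observed proportions for CBT (62% by" one cited trial, 64% by another). For LDX, the Background gives "Study 1: 40% versus 14%; Study 2: 36% versus 13%) at the end of 11 weeks of treatment", LDX first and placebo second.

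No section says how a participant without the month-3 EDE is scored for remission, and none plans imputation.

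**The concern.** Remission in Stage 1 rests on one interview. Someone who lacks it has no outcome, and the plan does not say whether that person counts as not remitted, is imputed, or is left out. The intent-to-treat label does not settle this.

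The missing interviews need not be unrelated to outcome. Under Withdrawal From Treatment, intensified binge eating and failure to comply with medication can lead to removal from the study. The Failure to Improve paragraphs in sections 10 and 11 provide for withdrawal of patients who deteriorate significantly. Such patients are unlikely remitters. The medication-compliance criterion cannot apply in the CBT-only arm, so dropout could also differ between arms.

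At stake are the size and significance of the remission comparison, and the Aim 2b predictor, moderator and mediator analyses that use the same outcome. An unstated scoring choice can be made after the data are seen.

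**Working it through.** **Step 1. Does the choice of model settle the matter?** Logistic regression at month 3 needs a month-3 outcome. A binary mixed model uses all observed values, but within Stage 1 these are baseline and month 3. Eligibility requires binge-eating disorder, so baseline remission is taken as zero for everyone and carries no information. With no intermediate EDE to borrow from, the mixed model also reduces to the participants interviewed at month 3.

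**Step 2. Reproduce the stated power.** Inputs from the Power Analysis: 60 per arm, two-sided alpha 0.025 (z = 2.2414), rates 0.63 and 0.35. Pooled two-proportion formula:

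power = Φ{ [ |p1 − p2|·√n − z·√(2·p̄·(1 − p̄)) ] / √(p1(1 − p1) + p2(1 − p2)) }

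- All 60 scored: p̄ = 0.49; (0.28 × 7.746 − 2.2414 × 0.7070) / 0.6787 = 0.861; power **80.5%**. This reproduces the plan's contrast.
- 48 per arm (60 × 0.8): (0.28 × 6.928 − 1.5846) / 0.6787 = 0.524; power **70%**.
- 60 per arm, dropouts scored not remitted: rates 0.8 × 0.63 = 0.504 and 0.8 × 0.35 = 0.280; (0.224 × 7.746 − 1.5475) / 0.672 = 0.279; power **61%**.

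The other stated contrast, 66% vs 38%, gives 80.6%, 70% and 60%. By comparison, the continuous effect d = 0.64 reproduces at 48 per arm: 0.64 × √24 − 2.2414 = 0.894, power 81%. So the continuous figure allows for dropout, while the remission figure reaches 80% only without it.

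**Step 3. How far can scoring move the result?** CBT vs LDX, 60 per arm, 24 missing in total (20%), uncorrected Pearson chi-square. Counts are rounded to the nearest whole remitter. The documents give no dropout by arm, so the unequal splits are hypothetical.

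| Observed rates, missing CBT / LDX | Completers | Missing = not remitted |
|---|---|---|
| near 62% vs 38%, 12 / 12 | 30/48 vs 18/48, p = 0.0143 | 30/60 vs 18/60, p = 0.0253 |
| near 63% vs 35%, 12 / 12 | 30/48 vs 17/48, p = 0.0079 | 30/60 vs 17/60, p = 0.015 |
| near 63% vs 35%, 16 / 8 | 28/44 vs 18/52, p = 0.0046 | 28/60 vs 18/60, p = 0.060 |
| near 63% vs 35%, 8 / 16 | 33/52 vs 15/44, p = 0.0041 | 33/60 vs 15/60, p = 0.0008 |

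In the four rows the differences go from 25 to 20, 27 to 22, 29 to 17, and 29 to 30 percentage points. The rates of 62% and 38% come from the documents' own figures: 62% is cited for CBT, and 38% lies midway between the 36% and 40% cited for LDX.

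**The case against.** Several objections have force.

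- **Dropout is not the same as a missing interview.** The 20% is a planning ceiling, supported partly by completion rates of 87% and 84% (13% to 16% dropout). The plan follows people who stop treatment, asks those taken off medication to continue assessments where applicable (Monitoring of Depressive Symptoms), pays $100 for the post-Stage 1 assessment and invites dropouts back for follow-up evaluations (section VI, item 2). A reader might infer that the plan expects a fifth of participants to lack the EDE; it does not say so. Equally, the Stage 2 power text treats dropouts as lacking complete data (80 become 64), and the monitoring section cites 20% to 38% attrition in earlier drug studies of this disorder. The missing fraction could be lower or higher than 20%.
- **The plan does not choose to delete anyone.** A reader might infer that it adopts a completers' analysis. Exclusion follows from the data structure and software defaults. The documents support only that no rule is stated and that two models are named without being reconciled.
- **The conclusion often does not change.** At 63% vs 35% with equal dropout, both p-values stay under 0.025. With fewer missing the same holds: 8 per arm gives 0.003 and 0.006 (33/52 vs 18/52; 33/60 vs 18/60), and 10 per arm gives 0.005 and 0.010 (32/50 vs 18/50; 32/60 vs 18/60). The crossing at 62% vs 38% is bare, and the large shift needs an assumed split.
- **Pattern mixture models are planned.** They are conditional, serve as sensitivity analyses and set no primary score for remission.

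These points limit the size of the problem. They do not supply the missing rule.

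**Conclusion.** The concern holds in a limited form. Stage 1 remission has two named models, one post-baseline interview and no rule for participants without it, so the intent-to-treat label is not met by either model as described. Under the plan's own rates and its 20% allowance, the handling of missing interviews can move p from 0.0143 to 0.0253 with balanced dropout. Under hypothetical two-to-one splits it can move p from 0.0046 to 0.060, or from 0.0041 to 0.0008. This shows that the result can depend on scoring, not that it will. Nor do the figures show that completer analysis always inflates the effect, since the last split moves it slightly the other way.

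The power figure is a firmer point: 63% vs 35% at alpha 0.025 has 80.5% power with all 60 per arm scored, 70% with 48, and 61% with 20% per arm scored as not remitted.

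Assumptions: 20% of interviews missing; 0.025 as the reference level, because the power section uses it for remission (Data Analysis applies a Bonferroni correction to secondary analyses without giving the number of tests); and unadjusted chi-square tests. Remission is a secondary outcome, so this should be corrected but does not threaten the co-primary analyses.

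**What to change.** In section 13, item (1):

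1. Name one model for month-3 remission: logistic regression in all randomised participants. Remove remission from the GLIMMIX sentence.
2. Multiply impute the missing month-3 EDE binge count, by arm, from the baseline EDE, the available monthly EDE-Q-I counts, the BDI-II and the randomisation strata. Dichotomise after imputation.
3. Prespecify one sensitivity analysis in which every missing month-3 remission is scored as not remitted.
4. Use the same remission outcome in Aim 2b.
5. In the Power Analysis, restate the remission power with the assumed fraction of missing interviews and their handling made explicit.

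The cost is SAP wording and a standard imputation step on data already collected. The estimate may move in either direction from the completer result, and the stated remission power will be less favourable. Scoring missing as not remitted in the primary analysis would also close the gap; imputation is preferred because it uses the monthly EDE-Q-I reports.
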